
6.0 CRITERIA FOR PARTICIPANT ELIGIBILITY

6.1 Participant Inclusion Criteria

1. Patients must be enrolled or agree to consent to the companion genomic profiling study MSKCC IRB# 12-245 Part A. Results are not required prior to

Memorial Sloan Kettering Cancer Center
[name]
[name]

initiating treatment on protocol, unless patients do not have other test results by IHC or FISH confirming HER2 overexpression.

2. Patients must have recurrent or persistent HER2 overexpressing endometrial cancer or endometrial carcinosarcoma. HER2 overexpression is defined as 3+ by IHC or 2+ with gene amplification by FISH (HER2/CEP17 ratio ≥ 2) or HER2 amplified (fold change ≥ 2) on MSK IMPACT.
3. Histologic documentation of diagnosis of endometrial carcinoma or carcinosarcoma is required.
4. Age ≥ 18 years
5. Patients must have had at least one but no more than two prior chemotherapeutic regimens for management of endometrial carcinoma (including neo-adjuvant and/or adjuvant chemotherapy). Initial treatment may include chemotherapy, chemotherapy and radiation therapy, and/or consolidation/maintenance therapy. Chemotherapy administered in conjunction with primary radiation as a radio-sensitizer WILL be counted as a systemic chemotherapy regimen. Prior hormonal therapy will **not** count as a prior regimen.
Prior treatment with trastuzumab is allowed.
6. Eastern Cooperative Oncology Group (ECOG) performance status of 0 or 1.
7. LVEF $\geq 50\%$ on baseline screening ECHO.
8. Resolution of adverse effects of recent surgery, radiotherapy, or chemotherapy to Grade ≤ 1 prior to first study treatment (with the exception of alopecia or clinically insignificant laboratory values).
9. Patients must have measurable disease. Measurable disease is defined by RECIST (version 1.1). Measurable disease is defined as at least one lesion that can be accurately measured in at least one dimension (longest diameter to be recorded). Each non-nodal lesion must be ≥ 10 mm when measured by CT, MRI or caliper measurement by clinical exam; or ≥ 20 mm when measured by chest x-ray. Lymph nodes must be ≥ 15 mm in short axis when measured by CT or MRI.
10. No active infection requiring antibiotics (with the exception of uncomplicated urinary tract infection).
11. All patients must consent to mandatory pre-treatment and post-treatment core needle biopsies.
12. Patients must have adequate hematological, liver, cardiac and kidney function within 14 days prior to first treatment:

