Survival Status ⁿ												● ⁿ

- a. Within 28 days prior to the start of Cycle 1, Day 1
- b. Directed physical examination is acceptable while on study treatment. Full examination is required at screening and the EOT visit.
- c. Within 14 days prior to the start of Cycle 1, Day 1
- d. Vital signs (blood pressure, pulse, respiration rate, and temperature) will be measured as outlined in the full protocol.
- e. Day 1 laboratory assessments may be performed up to 4 days prior to study agent administration. Laboratory results must be reviewed prior to each scheduled administration of ZW25, with the exception of coagulation testing (PT/INR, aPTT). In the event of severe toxicity, laboratory tests must be repeated as necessary until the toxicity resolves or stabilizes.
- f. For WCBP, a urine or serum pregnancy test will be performed at screening, prior to dosing on Day 1 of every cycle (it can be performed up to 14 days prior to Day 1) and at the 30-day Follow-Up visit. Additional testing may be performed in accordance with institutional requirements or local regulation.
- g. Patients will complete tumor assessments every 8 weeks (from C1D1) until Week 24, then every 12 weeks (± 1 week). If a patient discontinues prior to documentation of PD, a tumor assessment is to be performed at the End of Study visit or 30-Day Follow up visit, if not performed within the previous 6 weeks. Patients who have discontinued study treatment for reasons other than PD will be followed per RECIST 1.1 every 12 weeks (±3 weeks) until documentation of PD, starting a subsequent anti-cancer therapy or for up to one year from Cycle 1, Day 1, whichever comes first.
- h. As clinically indicated.
- i. All AEs and SAEs from the time of informed consent should be recorded.
- j. ECOG assessment is not necessary on Cycle 1 Day 1 if screening assessment was performed within 3 days prior
- k. For logistical reasons such as holidays, a +/- 3 day window applies to all study visits.
- l. Mandatory biopsy at screening and EOT (at time of progression of disease) within 14 days of EOT before initiating new treatment regimen.
- m. Research bloods include ADA and cfDNA sample collection. Research bloods can be collected at screening or cycle 1 day 1 before initiating treatment for baseline collections.

ADA will be collected at baseline and pre-dose at cycles 2, 4, 6, 8, 12, 18, 24 Day 1.

- n. Survival status' can be documented with a phone call or any clinic visits.

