HER2 targeted therapies have been associated with cardiotoxicity. Therefore, only patients who have baseline normal left ventricular ejection fraction and no history of significant cardiac disease will be eligible for treatment with ZW25. Patients with a lifetime cumulative dose of anthracycline >300 mg/m² or who have received anthracycline treatment within 90 days of the expected first dose of ZW25 are not eligible for treatment.

Patients are monitored per the study-specific protocol for changes in cardiac function. Cardiac monitoring includes assessment of ECG (frequency and type of abnormalities using standard 12-lead ECG, including heart rate, PR interval, QRS complex, QTcF), and echocardiogram (estimation of ejection fraction).

Management of decreased left ventricular ejection fraction (LVEF), regardless of relationship to study drug, is described in Table 3 below.

Table 3: Management Guidelines for LVEF Dysfunction

Left Ventricular Dysfunction	Management
Symptomatic cardiac heart failure	
• Discontinue ZW25
LVEF <40%	
• Do not administer ZW25• Repeat LVEF assessment within 4 weeks• If LVEF <40% is confirmed, discontinue ZW25
LVEF below institutional limits of normal and \geq 10% points below pre-treatment baseline	
• Do not administer ZW25• Repeat LVEF assessment within 4 weeks• If the LVEF has not recovered to within 10% points from baseline, discontinue ZW25
LVEF 40% to \leq 45% and decrease is $<$ 10% points from baseline	
• Continue treatment with ZW25• Repeat LVEF assessment within 4 weeks
LVEF $>$ 45%	
• Continue treatment with ZW25, as applicable

Gastrointestinal Toxicity

The most common ZW25-related gastrointestinal TEAEs ($>$ 20%) were diarrhea and nausea. Two patients in Part 1/2 developed ZW25-related Grade 3 diarrhea (20 mg/kg), which subsequently resolved with medications. No patients in Part 3 developed ZW25 Grade 3/4 gastrointestinal toxicity.

Table 4: Management Guidelines for Potential Infusion-related Reactions

Infusion Reaction CTCAE v5.0 Severity Grade	Management

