Mild to moderate diarrhea has been frequently reported in patients treated with ZW25. Patients will be prescribed loperamide as a prophylactic measure prior to Cycle 1 Day 1 of treatment and will be instructed on its use. Patient should be advised to contact their treating physician at the first sign of diarrhea and should be treated according to standard institutional practice. One suggested regimen would be the administration of 2-4mg of loperamide at the first sign of loose stool, with repeat dosing every 2 hours until symptoms resolve and up to a maximum of 16mg/day.⁴⁶ For Diarrhea that is G3 despite use of optimal anti-diarrheal treatment, hold drug until resolved to ≤ grade 1, then resume at a lower dose level.

Monitoring and Management of Nausea and Vomiting Following the Administration of ZW25

Nausea and vomiting have been reported in patients treated with ZW25. Patients should be advised to contact their treating physician at the first sign of vomiting or worsening nausea. Patients should be treated according to the American Society of Clinical Oncology (ASCO) Clinical Practice Guidelines for the use of antiemetics⁴⁷ outlined in Table 5.

Table 5: Management of Nausea and Vomiting

Severity Grade (CTCAE v5.0 Grade)	Management
Grade 1	Administer single 8 mg dose of dexamethasone before therapy
Grade 2	Administer a 5- HT ₃ receptor antagonist on day 1 (e.g. palonosetron, granisetron, or ondansetron) in combination with dexamethasone on days 1-3 or treat as per institutional guidelines. Aprepitant may be added to the combination.
Grades 3 and 4	Administer a neurokinin 1 receptor antagonist (e.g. aprepitant on days 1-3 or fosaprepitant on day 1), in combination with a 5-HT ₃ receptor antagonist on day 1 only, and dexamethasone on days 1-3 or 1-4 or treat as per institutional guidelines. For G3 nausea/vomiting despite optimal use of antiemetics, hold drug until resolved to ≤ grade 1, then resume at a lower dose level.

Other non-hematological toxicities: Except adverse events related to underlying disease, Grade 3 fatigue, isolated symptomatic G3 biochemistry abnormalities that last for < 7 days including electrolyte abnormalities that respond to medical intervention, for a Grade 3 event, hold study drug until resolved to ≤ Grade 1, then resume at lower level. For any grade ≥ 3 cardiac events and for Grade 4, non-hematological toxicities, permanently discontinue ZW25 treatment.

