For any Grade 3 hepatic toxicity that does not resolve to baseline within 7 days, an abdominal CT scan must be performed to assess whether it is related to disease progression.

Re-treatment Criteria

To Begin a New Cycle of Treatment or continue treatment within a cycle

For a patient to begin a new cycle or continue a cycle of therapy, the following criteria must be met.

- ANC must be ≥ 1.0x10⁹/L (1,000/µL)
- Platelet count must be ≥ 75 x 10⁹/L (75,000/µL)

- All non-hematologic toxicities for which a causal association to study treatment cannot be ruled out, must be \leq Grade 1 (except alopecia) or returned to baseline.
- If the patient does not meet these criteria, dosing will be delayed and the patient should be re-evaluated within 48-72 hours. Dosing will resume if these criteria have been met.

If treatment is delayed due to treatment-related toxicity longer than one cycle, then the patient should be removed from study treatment. In such cases, continuation of study treatment may be considered for those patients who have experienced clinical benefit if agreed upon by the principal investigator and Zymeworks.

The use of granulocyte growth factors in accordance with ASCO guidelines may be implemented at the discretion of the treating physician.

Follow-up for AEs Leading to Discontinuation

Patients who discontinue study treatment for an AE or an abnormal laboratory value must be followed at least once a week for 4 weeks, and subsequently at 4-week intervals until resolution or stabilization of the adverse event or laboratory abnormality, whichever occurs first.

Dose Modification Guidelines

ZW25 Dose Reduction Following an AE

ZW25 dose may be reduced at the discretion of the Investigator after discussion with Zymeworks. Patients who develop adverse events requiring an interruption of ZW25 may resume treatment at a reduced dose level as shown in Table 6.

Table 6: ZW25 Dose Modification Guidelines

Regimen	If the patient was receiving ZW25 at:
Dose Level 1	20mg/kg intravenously (IV) every two weeks
Dose Level -1	15 mg/kg every two weeks
Dose Level -2	10 mg/kg every two weeks

**Reduction of the ZW25 dose below 10 mg/kg will not be permitted.*

Overdose and Medication Error

Overdose: There is no known treatment/antidote available for ZW25. Supportive measures should be instituted if an instance arises in which a patient suffers an overdose of any study drug.

Memorial Sloan Kettering Cancer Center
[name]
[name]

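### Section 15.0 exempts brief isolated Grade 3 laboratory abnormalities from hold-and-reduce only when they are symptomatic; one word is very likely reversed

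*Combined protocol and SAP*

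**What the plan says.** The rule is in Section 15.0, in the paragraph headed Other non-hematological toxicities. Its instruction is "for a Grade 3 event, hold study drug until resolved to ≤ Grade 1, then resume at lower level". Three kinds of event are taken out of it: events due to the underlying disease, Grade 3 fatigue, and "isolated symptomatic G3 biochemistry abnormalities that last for < 7 days including electrolyte abnormalities that respond to medical intervention".

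Four other places bear on how it works:

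- **Re-treatment Criteria (Section 15.0).** Before any dose, "All non-hematologic toxicities for which a causal association to study treatment cannot be ruled out" must be at Grade 1 or lower, or back to baseline. Otherwise dosing is delayed.
- **Dose Modification Guidelines and Table 6 (Section 15.0).** The level below 20 mg/kg is "15 mg/kg every two weeks", then 10 mg/kg, and "Reduction of the ZW25 dose below 10 mg/kg will not be permitted". The text above the table is permissive: the investigator can lower the dose after talking to the drug supplier, and a patient whose treatment was interrupted can restart at a lower level.
- **Schedule of assessments (Section 11.0, footnote e).** "Laboratory results must be reviewed prior to each scheduled administration of ZW25", coagulation tests excepted.
- **Inclusion criterion 8 (Section 6.1).** Recovery from earlier treatment to Grade 1 is required "with the exception of alopecia or clinically insignificant laboratory values".

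**The concern.** An exemption of this kind normally spares patients a dose cut for a laboratory finding of little clinical weight. Here the presence of symptoms is a condition for leniency. The patient who feels the abnormality is exempt, and the patient in whom it is only a number on a report is not.

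This is an operative dosing instruction. A site that follows it to the letter would lower the dose for a short-lived, silent laboratory abnormality, the kind that the required review of results before each infusion can pick up. The same site would have no such instruction for the symptomatic counterpart.

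**Working it through.** No figure in the plan needs reproducing. The check applies the text to two patients who differ in one respect only.

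**Setup.** Each has an isolated Grade 3 biochemistry abnormality lasting under 7 days, not due to the underlying disease, while on 20 mg/kg. One has symptoms and the other does not.

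| Text in Section 15.0 | Symptomatic | Asymptomatic |
|---|---|---|
| Other non-hematological toxicities | Exempt: neither hold nor reduction instructed | Fits no exemption: hold to Grade 1 or lower, resume at a lower level |
| Re-treatment Criteria, if possibly related | Delay to Grade 1 or lower, or baseline | The same |
| Dose Modification Guidelines | Reduction permitted | Reduction permitted |

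**Result.** The rows agree except the first. For a possibly related event, the re-treatment criteria delay the next dose in both patients, so what differs is the instruction to come back at a lower level. For an event judged unrelated to treatment, the hold differs as well, because the Grade 3 paragraph excludes only events due to the underlying disease.

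**Size of one step (Table 6).** From 20 to 15 mg/kg: (20 - 15)/20 = 25%. A further step, from 15 to 10 mg/kg, would be (15 - 10)/15 = 33% and reaches the floor.

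**Is the word likely to be wrong?** The strongest evidence is inside the exemption. Each of the other qualifiers (isolated, under 7 days, responsive to treatment) narrows it to minor events. *Symptomatic* is the only one that narrows it to the more serious case. With *asymptomatic*, all the qualifiers point the same way and both outcomes in the first row swap. Inclusion criterion 8 is consistent with this but is weaker evidence: it is an eligibility rule, and clinically insignificant does not mean the same as asymptomatic.

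**Electrolytes.** The phrase on electrolyte abnormalities can be read as an example of the exempt class or as an exemption of its own. On the second reading, a treatable electrolyte abnormality is exempt whatever the symptoms, and the reversal touches only other chemistry.

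**Correction elsewhere.** No other text in the protocol restates or corrects the condition.

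**The case against.** The strongest reply is that little follows in practice. Much of it stands.

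- **Reduction is optional.** The Dose Modification Guidelines leave reduction to the investigator, so a reader who infers that every asymptomatic case must lose 25% of the dose goes too far. The Grade 3 paragraph is nevertheless imperative, and the diarrhea and nausea guidance uses the same form of instruction. The two texts are in tension, and a site could follow either.
- **The symptomatic patient is protected.** A reader might infer that such a patient is dosed through the toxicity. For possibly related events the re-treatment criteria prevent this, and the investigator remains free to reduce. In addition, Section 5.1 requires at least 12 days between doses, so an event lasting under 7 days will often be over before the next infusion.
- **The protocol spares some symptomatic toxicity.** Grade 3 fatigue is exempt in the same sentence. That is true, but it is a named term and does not explain why symptoms should be required before a laboratory finding is spared.
- **Table 3.** It is tempting to cite discontinuation for "Symptomatic cardiac heart failure", set against continued treatment for a modest LVEF fall, as a pattern. The table does not support that. It also withholds drug for LVEF under 40%, and for LVEF below normal with a fall of at least 10 points, with no symptom condition in either row.
- **Frequency.** The only related Grade 3 biochemistry event named in the phase 1 summary is one hypophosphatemia (1/67 = 1.5%). A reader might scale this to 25 x 1/67 = 0.4 patients here. That event is an electrolyte abnormality and may be exempt anyway, and its symptoms and duration are not given. A ceiling built by counting all unlisted Grade 3 or higher events as biochemistry would have no support in the text.

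**Conclusion.** Wrong as written; minor severity. As printed, the symptom condition gives the clinically worse case the more lenient instruction. The affected content is mainly the direction to resume at a lower level (20 to 15 mg/kg), and that direction already conflicts with permissive wording in the same section.

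Two assumptions limit this. First, that *asymptomatic* was intended is an inference from the exemption's other qualifiers; it is very likely but not stated. Second, the reach depends on how the electrolyte phrase is read. The number of patients affected is probably low and cannot be estimated from the documents. A reader might infer some loss of efficacy through lower doses, but nothing in the documents supports an effect on the response rate, the power or the primary test.

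**What to change.** Check the word against the source protocol file and ask the clinical team to confirm the intent. If confirmed, change *symptomatic* to *asymptomatic* in the paragraph on other non-hematological toxicities, so that brief, isolated, asymptomatic Grade 3 abnormalities are exempt and symptomatic ones come under hold-and-reduce. Leave the re-treatment criteria unchanged.

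The cost is one word in the next amendment, with no added procedures, visits or patients.

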15.1 Serious Adverse Event (SAE) Reporting

An adverse event is considered serious if it results in ANY of the following outcomes:

- Death
- A life-threatening adverse event
- An adverse event that results in inpatient hospitalization or prolongation of existing hospitalization
- A persistent or significant incapacity or substantial disruption of the ability to conduct normal life functions
- A congenital anomaly/birth defect
- Important Medical Events (IME) that may not result in death, be life threatening, or require hospitalization may be considered serious when, based upon medical judgment, they may jeopardize the patient or participant and may require medical or surgical intervention to prevent one of the outcomes listed in this definition

Note: Hospital admission for a planned procedure/disease treatment is not considered an SAE.

SAE reporting is required as soon as the participant starts investigational treatment/intervention. SAE reporting is required for 30-days after the participant's last investigational treatment/intervention. Any event that occurs after the 30-day period that is unexpected and at least possibly related to protocol treatment must be reported.

Please note: Any SAE that occurs prior to the start of investigational treatment/intervention and is related to a screening test or procedure (i.e., a screening biopsy) must be reported.

All SAEs must be submitted in PIMS. If an SAE requires submission to the HRPP office per IRB SOP RR-408 'Reporting of Serious Adverse Events', the SAE report must be submitted within 5 calendar days of the event. All other SAEs must be submitted within 30 calendar days of the event.

The report should contain the following information:

- The date the adverse event occurred

Memorial Sloan Kettering Cancer Center
[name]
[name]

- The adverse event
- The grade of the event
- Relationship of the adverse event to the treatment(s)
- If the AE was expected
- Detailed text that includes the following
 - An explanation of how the AE was handled
 - A description of the participant's condition
 - Indication if the participant remains on the study
- If an amendment will need to be made to the protocol and/or consent form
- If the SAE is an Unanticipated Problem

15.2. External SAE Reporting

For IND/IDE protocols:

The SAE report should be completed as per above instructions. If appropriate, the report will be forwarded to the FDA by the IND Office

15.2.1 Pharmaceutical Specific Reporting

Recording Adverse Events and Serious Adverse Events

AEs (including SAEs) will be documented on the AE eCRF and monitored continuously throughout the study from the time of informed consent until 30 days after the patient's last study treatment or until the event has resolved or stabilized or becomes chronic, whichever comes first. AEs attributed to study procedures should also be documented on the AE eCRF.

15.2.2 Adverse Events of Special Interest (AESI)

An adverse event of special interest (AESI) (serious or non-serious) is one of scientific and medical concern specific to the Grantor's product for which ongoing monitoring and rapid communication by the investigator to the Grantor could be appropriate. These include infusion-related reactions, non-infectious pulmonary toxicities, and cardiac-events of absolute decrease in LVEF of ≥ 10 percentage points from pretreatment baseline and absolute value $<50\%$ and/or grade ≥ 2 heart failure. These are reportable to the Grantor via monthly listings, unless they are serious and assessed by the investigator as Related to zanidatamab, in which case they are reportable to Zymeworks Drug Safety in an expedited manner using a CIOMS-I form.

The Investigator will promptly supply all information identified and requested by the Grantor regarding the SAE, AESI, or pregnancy.

Reporting to Zymeworks

Any SAE assessed by the Investigator as Related to a zanidatamab or pregnancy that occurs in a study subject between the time of first study drug administration and 30 days after last study drug administration will be reported to Zymeworks Drug Safety

([contact]) within 24 hours of first awareness of the event. For SAE reporting, including those that are expedited, completed CIOMS-I forms will be provided to Zymeworks. Any SAEs assessed by the Investigator as NOT Related to zanidatamab should be reported to Zymeworks via monthly listings.

Any SAEs deemed related to zanidatamab occurring beyond 30 days after the last study drug administration should be reported to Zymeworks ([contact]).

SADRs

A full report for SAEs that are related to the Product shall be transmitted to Zymeworks on a CIOMS-I form within 24 hours of the awareness date.

Other SAEs

SAEs that are unrelated to the Product shall be transmitted to Zymeworks within thirty (30) calendar days of the awareness date via monthly listings.

AESIs

Non-serious AESIs shall be forwarded to Zymeworks within thirty (30) calendar days of the awareness date via monthly listings.

Pregnancy reports

While such reports are not serious AEs or Adverse Drug Reactions (ADRs) per se, as defined herein, any reports of pregnancy where the fetus may have been exposed to the Product, shall be transmitted to Zymeworks within 24 hours of the awareness date.

Pregnancies will be followed up until the outcome of the pregnancy is known, whenever possible, based upon due diligence taken to obtain the follow-up information.

Reporting a Pregnancy

Pregnancy and lactation are exclusion criteria. Zymeworks must be immediately notified in the event of a pregnancy occurring during the course of the study and through 7 months after a patient's last dose of ZW25 whichever is earlier. Pregnancy is not to be reported as an AE; the CIOMS-I form should be used to report a pregnancy. All reported pregnancies must be followed to the completion/termination of the pregnancy.

Pregnancy outcomes of spontaneous abortion, missed abortion, benign hydatidiform mole, blighted ovum, fetal death, intrauterine death, miscarriage and stillbirth must be reported as serious adverse events (Important Medical Events). The reporting procedures will be followed, including pregnancies and pregnancy outcomes listed above are reportable to Zymeworks in the same timeframe as SAEs which are assessed by the investigator as Related to zanidatamab. If the pregnancy continues to term, the outcome (health of infant) must also be reported.

